4.3 EXCLUSION CRITERIA

A patient will be ineligible for inclusion in this study if **he or she** meets **any** of the following criteria:

- 1. Have a family history of long QT Syndrome and serious cardiac conditions.
- 2. Have QTcF interval of >470 msec on screening electrocardiogram (ECG) as well as on predose Cycle 1 Day 1 ECG.
- 3. Have insulin-dependent diabetes mellitus. Patients with a type 2 diabetes mellitus are eligible if adequate control of blood glucose level is obtained by oral anti-diabetics as documented by HbA1c <8%. Patients with type 1 diabetes mellitus are not eligible.
- 4. Previous radiotherapy for metastatic disease completed <2 weeks prior to study treatment initiation.
- 5. Women who are pregnant or lactating.
- 6. Patients who have any severe and/or uncontrolled medical conditions or other conditions that could affect their participation such as:
 - a. severe impaired lung functions as defined as spirometry and DLCO that is 50% of the normal predicted value and/or O₂ saturation that is 88% or less at rest on room air
 - b. liver disease such as cirrhosis or severe hepatic impairment (Child-Pugh class C).
 - c. viral hepatitis or HIV.
- 7. Concurrent use of CYP3A4 inhibitors and inducers from 72 hours prior to initiation of study treatment until the end of treatment.
- 8. History of any other disease, physical examination finding, or clinical laboratory finding giving reasonable suspicion of a disease or condition that contraindicates use of an investigational drug, or that might affect interpretation of the results of this study, or render the patient at high risk for treatment complications.
- 9. Patients who have received prior PI3K or CHK therapy.

- 10. Any other investigational or anti-cancer treatments while participating in this study
- 11. Any other active malignancy

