6.2.5 Adverse Effects

The safety profile of prexasertib is consistent with toxicities commonly observed with standard-of-care cytotoxic agents used to treat cancer (for example, neutropenia, thrombocytopenia, and anemia). Complications from these toxicities such as febrile neutropenia, infections, and clinically significant bleeding events can be mitigated by supportive care approaches such as administration of granulocyte-colony-stimulating factor (G-CSF) and transfusions. Nonhematologic toxicities deemed related to prexasertib treatment occur at a much lower frequency and severity, with fatigue, nausea, diarrhea, decreased appetite, and vomiting being the mostly commonly observed events. Infusion-related reactions have been observed in patients who received prexasertib. For further details, please refer to the prexasertib Investigator's Brochure.²⁷

Prexasertib and QTc

In nonclinical toxicology studies in dogs, dose-progressive prolongation of QRS duration and QTc interval was observed. Across Studies JTJA and JTJK, the largest mean QTcF increases from baseline (<15 ms) occurred at the end of the prexasertib infusion. On average, increases in

QTcF values from baseline were <10 ms 1 to 2 hours following the end of infusion and returned to predose values within approximately 24 hours. Taken together, since prexasertib is given IV and concentrations decline quickly after the end of infusion, the observed QTcF changes would be transient in nature and are not considered an important risk to patients at this time.

In Study JTJA, the maximal QTcF increase from baseline was 39 ms and no event of QTcF prolongation was associated with an SAE. Across the program, Torsades de Pointes or serious arrhythmias have not been reported.

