Electrocardiograms should be evaluated for changes in QT/QTc interval. Patients with additional risk factors for Torsades de Pointes, including heart failure, a prolonged QTc interval >470 ms on screening ECG, or a family history of long QT syndrome, should be excluded from clinical trials. On days when prexasertib is administered, patients should avoid taking multiple (more than 1) concomitant medications that are known or suspected to cause prolonged QTc or Torsades de Pointes and, if possible, alternative agents should be considered. In addition, at the start of the study and on days when prexasertib is administered, care should be taken to ensure that there are no abnormal levels of electrolytes that could increase the risk for ECG changes.²⁷

Pregnancy

The potential treatment effects of prexasertib use during pregnancy and lactation are not known. Nonclinical studies of prexasertib on pregnancy and fetal development have not been performed. To minimize any potential risks, men and women with reproductive potential should use medically approved contraceptive precautions during treatment and for 3 months after the last dose of prexasertib.²⁷

Nursing Mothers

The potential treatment effects of prexasertib use during lactation are not known. Women who are breastfeeding should not receive prexasertib.²⁷

Please see the Investigator's Brochure for additional adverse events and complete drug information.

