7.2.4 Dose Modification for Toxicity

Dose reductions are to be made according to the system showing the greatest degree of toxicity. Toxicities will be graded according to the NCI Common Terminology Criteria for Adverse Events (CTCAE) Version 4.03 as linked in Appendix I. At each clinic visit, treatment with LY3023414 or with prexasertib will continue if:

- ANC ≥1000 (if pegfilgrastim is being used) or of ≥1200/mm³ (if no pegfilgrastim is being used)
- Platelets \geq 75,000/mm³
- Resolution of nonhematologic toxicities to \(\le \) Grade 1 or baseline

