8 SCHEDULE OF ASSESSMENTS

The schedule of assessments for the trial is shown in Appendix II. If a required observation or procedure is missed, documentation is required in the source records, on the Protocol Deviation Form, and on the CRF, to explain the reason for this protocol deviation.

^b Except alopecia, fatigue, or toxicities that can be controlled with adequate treatment such as nausea, vomiting, diarrhea, or asymptomatic electrolyte disturbances.

^c Baseline is considered prior to dosing on Cycle 1 Day 1.

For scheduling purposes, Day 1 is the first day of treatment administration. Return appointments must always be scheduled from Day 1 of the study. It is imperative that all visits occur within the specified windows.

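### Exclusion 2, read literally, requires QTcF above 470 msec on both ECGs, which conflicts with section 6.2.5; it should say either ECG, and exclusion 1 should be aligned

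*Combined protocol and SAP*

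**What the plan says.** Section 4.3 lists eleven exclusions, and the synopsis repeats them. Four bear on this point.

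- Exclusion 1: "Have a family history of long QT Syndrome and serious cardiac conditions".
- Exclusion 2: "Have QTcF interval of >470 msec on screening electrocardiogram (ECG) as well as on predose Cycle 1 Day 1 ECG".
- Exclusion 6, a general clause: "Patients who have any severe and/or uncontrolled medical conditions or other conditions that could affect their participation such as". Its examples are lung impairment, liver disease, viral hepatitis and HIV; none is cardiac.
- Exclusion 8, a second general clause, which reaches findings that would "render the patient at high risk for treatment complications".

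The prexasertib safety text in section 6.2.5 covers the same ground. It would keep anyone at added risk of Torsades de Pointes out of trials, and its key words are: "including heart failure, a prolonged QTc interval >470 ms on screening ECG, or a family history of long QT syndrome, should be excluded". It also gives the size of the concern: "the observed QTcF changes would be transient in nature and are not considered an important risk to patients at this time".

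Section 8.1 determines eligibility before entry from sections 4.2 and 4.3, and places the screening ECG within 4 weeks before registration. Section 7.1 assigns the patient number once the patient is found eligible, treats that as registration, and allows up to 20 working days from then to first treatment. Section 8.2 places the predose ECG within 10 minutes of the start of the prexasertib infusion.

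**The concern.** Exclusion 2 joins two ECGs with a phrase that normally means both. A coordinator who applies it as written would exclude only a patient above 470 msec twice. The protocol's own drug-safety section says once, at screening, is enough.

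Sections 4.2 and 4.3 are what is checked at entry; section 6.2.5 is background on the drug. If the two disagree, the checklist is likely to be followed. A patient could then be enrolled whom the safety section would keep out, and a patient whose QTcF is first seen to be high just before the first infusion would meet no stated limit. What is at stake is the safety of individual patients, not the estimate of the response rate.

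**Working it through.** No arithmetic is needed to establish the conflict. The check sets the sections against each other for every combination of the two ECG results. It takes the QTcF of section 4.3 and the QTc of section 6.2.5 to be the same measure.

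| Screening above 470 | Predose Day 1 above 470 | Exclusion 2, literal (both) | Exclusion 2 as a limit at each ECG | Section 6.2.5 |
|---|---|---|---|---|
| yes | yes | excluded | excluded | excluded |
| yes | no | **admitted** | excluded | **excluded** |
| no | yes | **admitted** | excluded | silent: names only the screening ECG |
| no | no | admitted | admitted | no bar |

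**Second row.** This is the conflict: the literal exclusion admits and section 6.2.5 excludes.

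**Third row.** This is the gap. Three other places could have supplied a Day 1 limit, and none does:

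- Section 8.2 requires the predose ECG and says that predose assessments may decide whether drug is given, but states no QTc value.
- Section 7.2.4 begins "At each clinic visit, treatment with LY3023414 or with prexasertib will continue if" and lists neutrophils, platelets and resolution of nonhematologic toxicity.
- Section 4.4, on reasons off treatment, has no QTc criterion.

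**Timing.** The screening ECG can be 4 weeks old at registration. Treatment can start 20 working days later, and 20 / 5 = 4 calendar weeks. So the screening ECG can be about 4 + 4 = 8 weeks old at first dose, and the Day 1 ECG deserves a limit of its own. The same timing shows that a rule needing both ECGs cannot be completed at registration, because the second ECG does not yet exist.

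**Exclusion 1.** Its 'and' allows three readings:

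| Reading | Family history of long QT syndrome only | Patient's own heart failure only |
|---|---|---|
| Both conditions needed together | admitted | admitted |
| Family history of both | admitted | admitted |
| Two separate exclusions | excluded | excluded, if heart failure counts as serious |
| Section 6.2.5 | excluded | excluded |

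Only the third reading agrees with section 6.2.5. Section 4.3 nowhere names heart failure.

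**The case against.** The strongest reply is that the literal reading is the less plausible one. Under it, a screening ECG could never exclude anyone and exclusion 2 could not be applied at registration, although section 8.1 requires confirmation before entry that no exclusion is met. Reading it as a limit checked at each ECG avoids both problems and agrees with section 6.2.5. That is persuasive about intent. It does not remove the defect, because the sentence still does not say so, and writing *or* costs the sponsor nothing if that was the intent.

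A second reply is that patients are protected anyway. Section 6.2.5 is part of the same protocol, exclusions 6 and 8 can catch high-risk patients, section 8.2 lets predose findings stop a dose, and section 4.4 allows a physician to stop treatment. These safeguards are real and reduce the risk. Except for section 6.2.5, which is one side of the conflict, they all rest on judgment and none gives a QTc threshold.

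A reader might also infer that the protocol makes a high Day 1 QTcF acceptable, because a note to Table 4 says "Baseline is considered prior to dosing on Cycle 1 Day 1". The documents do not support this. The note belongs to the Table 4 rows on other nonhematologic toxicity and concerns recovery during treatment. A QTcF recorded before any study drug is not a treatment toxicity, and the note says nothing about eligibility for a first dose.

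**Conclusion.** The point holds as a wording defect with a minor safety consequence. Read literally, exclusion 2 contradicts section 6.2.5 for a patient high at screening only, and leaves no stated limit for a patient first high on Day 1. Exclusion 1 is ambiguous rather than wrong.

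The number of patients affected cannot be derived, because the documents give no frequency of QTcF above 470 msec. The effect of prexasertib described in section 6.2.5 is small and brief. The largest mean QTcF increases were below 15 ms, at the end of infusion, with return to predose values within about 24 hours. The maximum increase in Study JTJA was 39 ms. No Torsades de Pointes or serious arrhythmia was reported across the program.

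A reader might infer two stronger conclusions, and neither is supported:

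- **That the protocol deliberately admits patients with a prolonged QTc.** Section 6.2.5 and the timing of the ECGs both point to an intended limit at each ECG.
- **That the defect weakens the decision rule on ten patients.** Section 11.4 bases the rule on patients enrolled and treated, and section 11.1.1 requires at least one dose for the evaluable population. The wording affects who may enter, not the endpoint, the analysis or the operating characteristics.

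**What to change.** Make two edits, each in section 4.3 and in the synopsis.

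- Item 1: *Have a family history of long QT syndrome, or have heart failure or another serious cardiac condition.*
- Item 2: *Have QTcF >470 msec on the screening ECG or on the predose Cycle 1 Day 1 ECG (a high Day 1 value may be repeated after electrolyte correction within the 20-working-day window before first dose).*

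The repeat keeps a single high reading from excluding a patient whose electrolytes can be corrected. It fits section 6.2.5, which asks for care over electrolytes at the start of the study, and the window in section 7.1.

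The cost is a few words in two places. The downside is an occasional extra exclusion, sometimes after the patient has been registered, and now and then a first dose delayed within the allowed window. Section 11 needs no change.

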4.2 INCLUSION CRITERIA

A patient will be eligible for inclusion in this study if **he or she** meets **all** of the following criteria:

- 1. Patients ≥18 years of age. Patients must agree to use one highly effective (less than 1% failure rate) method of contraception or use a combination of two effective methods of contraception during treatment with study drug and for at least 12 weeks following the last dose of study drug.
- 2. Have a diagnosis of metastatic TNBC previously treated with standard anthracycline, cyclophosphamide, and taxane chemotherapy, unless there was a contraindication to doxorubicin, in which case prior treatment with this agent is not required. **NOTE:** TNBC defined as ER-negative tumors with ≤10% tumor nuclei immunoreactivity, or "ER Low Positive" as defined by the updated ASCO/CAP guidelines 2020.²⁵
- 3. Have not received more than 3 prior chemotherapy regimens for metastatic disease. Prior platinum and/or taxane therapy in the adjuvant or metastatic setting is permitted.
- 4. Have locoregional (eg, breast, chest wall, regional lymphatic) or pulmonary or hepatic metastatic disease that is amenable to core needle biopsy. If a research biopsy from a patient's metastatic disease cannot be safely obtained, a skin biopsy is permitted. If a skin biopsy cannot be safely obtained, patients may still be eligible, per physician discretion.
- 5. Have an Eastern Cooperative Oncology Group (ECOG) performance status of 0-2 (See Appendix I)
- 6. Have adequate hematologic function, defined by:
 - a. Absolute neutrophil count (ANC) >1500/mm³
 - b. Platelet count $\geq 100,000/\text{mm}^3$
 - c. Hemoglobin ≥9 g/dL
- 7. Have adequate liver function, defined by:
 - a. AST and ALT \leq 2.5 x the upper limit of normal (ULN) or \leq 5 x ULN in presence of liver metastases

- b. Total bilirubin ≤1.5 x ULN
- 8. Have adequate renal function, defined by:
 - a. Serum creatinine ≤ 1.5 x ULN or calculated creatinine clearance of ≥ 60 ml/min
- 9. Have the ability to swallow oral medications
- 10. Patients who have a history of brain metastasis are eligible for the study provided that all the following criteria are met:
 - a. Brain metastases which have been treated
 - b. Off-treatment with steroids for 2 weeks before administration of the first doses of LY3023414 and prexasertib
 - c. No ongoing requirement for dexamethasone or anti-epileptic drugs
 - d. No clinical or radiological evidence of progression of brain metastases

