7 INVESTIGATIONAL PLAN

7.1 REGISTRATION PROCEDURES

Written documentation of full, noncontingent IRB approval must be on file before a patient can be registered. The registration process begins when the Coordinator has obtained a signed informed consent.

A patient identification number is directly assigned once the patient is found eligible. Patient ID, consent date, status of patient (eg, active or screen failure), relevant comments, and date of patient discontinuation are to be recorded on the Patient Log by the Coordinator. The Patient Log will be kept in a binder for review for any reason (ie, monitoring/audit). Once a patient ID is assigned, this will constitute the registration confirmation. **Treatment must begin within 20 working days (not counting the day of dosing) after the patient's registration on the study.**

The PI may be allowed the opportunity to review and grant exceptions for minor deviations in eligibility, in order to maximize patient accrual without jeopardizing patient safety or scientific integrity of these studies. Examples might include minor deviations of baseline labs, timing of prior treatment or tests, etc. It is recognized that these questions arise frequently. The procedure to be followed is for the Investigator or his/her representative (eg, research nurse) to e-mail the request to the PI for an exception. The PI would then make a determination, which is binding. In no instance should this exception constitute a safety issue for the patient or a significant deviation from the scientific purpose of the study.

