- 15. A clinical assessment of the patient's disease (ie, by physical examination) must be performed within 4 weeks prior to registration.

- 16. Radiological assessment of tumors (ie, chest and abdomen CT scan) must be performed within 8 weeks prior to registration. The methods used for prestudy assessments should be used throughout the study. If possible, the same equipment should be used each time.
- 17. Assessments of other lesions by physical exam must be performed within 4 weeks prior to registration.
- 18. If safely accessible, research biopsies of the patient's metastatic locoregional or pulmonary or hepatic disease must be obtained **prior to the first day of treatment**. If a research biopsy from a patient's metastatic disease cannot be safely obtained, a skin biopsy is permitted. If a skin biopsy cannot be safely obtained, patients may still be eligible, per physician discretion.
- 19. Whole blood collection (40 mL) for germline exome sequencing studies.
- 20. Distribution of LY3023414 dosing and treatment adverse events patient diaries (see Appendix V).

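### No interval is set after systemic anticancer therapy, and the baseline scan may precede the last prior dose, so shrinkage from earlier treatment can be counted in the single-arm response rate

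*Combined protocol and SAP*

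**What the plan says.** Prior treatment is governed by Sections 4.2 and 4.3, repeated in the synopsis.

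- Inclusion 2: "Have a diagnosis of metastatic TNBC previously treated with standard anthracycline, cyclophosphamide, and taxane chemotherapy", with an allowance where doxorubicin was contraindicated.
- Inclusion 3: "Have not received more than 3 prior chemotherapy regimens for metastatic disease".
- Exclusion 4: "Previous radiotherapy for metastatic disease completed <2 weeks prior to study treatment initiation".
- Exclusion 10: "Any other investigational or anti-cancer treatments while participating in this study". Section 5 likewise restricts other anticancer drugs only for the study period.

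Two further pre-dose intervals concern drugs that are not anticancer therapy: exclusion 7, "Concurrent use of CYP3A4 inhibitors and inducers from 72 hours prior to initiation of study treatment until the end of treatment", and, for patients with a history of brain metastasis, inclusion 10b, "Off-treatment with steroids for 2 weeks before administration of the first doses of LY3023414 and prexasertib".

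Section 8.1 says the chest and abdomen CT "must be performed within 8 weeks prior to registration". It does not tie the scan to the last dose of earlier therapy. Section 7.1 allows up to 20 working days from registration to first dose, sets no minimum, and lets the principal investigator grant minor eligibility exceptions: "Examples might include minor deviations of baseline labs, timing of prior treatment or tests, etc".

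The primary objective is the objective response rate (Section 2.1), assessed by the investigator (Section 10). Under Section 11.4, 0 or 1 response in 10 stops enrolment, and 2 or more allow an expansion to 20 to be considered.

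**The concern.** A patient whose disease was stable or shrinking on chemotherapy, and who stopped for tolerability shortly before registration, can satisfy the prior-treatment criteria. Earlier therapy can then appear as study response by two routes:

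1. **Baseline before the last prior dose.** Chemotherapy given between the baseline CT and registration is not excluded. Shrinkage that it causes before the first study dose is measured from the older, larger baseline.
2. **Residual effect.** Even with a CT taken the day before dosing, a recent systemic drug can go on shrinking lesions during Cycle 1 and later.

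With no control arm, neither can be separated from the effect of the combination. With ten patients and a threshold of two responses, a single such patient matters.

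**Working it through.** **Plan's own figure.** Section 11.4 gives a 60% chance of 4 or more responses in 20 at a true rate of 20%. Exact binomial: 1 − (0.0115 + 0.0576 + 0.1369 + 0.2054) = 0.589. The figure is reproduced to within rounding.

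**Age of the baseline scan.** 8 weeks before registration (Section 8.1) plus 20 working days, about 4 weeks (Section 7.1): 56 + 28 = 84 days, or about 12 weeks before first dose.

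**Does another rule close the gap?**

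- Exclusion 10 and Section 5 act during the study, so they do not reach a dose given just before it.
- Exclusion 9 bars only prior PI3K or CHK therapy.
- Exclusion 8 concerns diseases and findings, not recent treatment.
- Section 8.2 requires prestudy assessments older than 72 hours to be repeated for Cycle 1. That renews the physical-examination assessment. Imaging has its own schedule there (every 8 weeks or as clinically indicated). Even a repeated CT would close only the first route.

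**Effect on the expansion threshold.** The documents give neither a carry-over frequency nor the true rate, so true rates t of 5% to 25% are assumed. This range includes the 20% used in Section 11.4 and the 25% partial-response figure for TNBC in Section 1.5.

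- No carry-over: P(X ≥ 2, n = 10) = 1 − (1 − t)^10 − 10t(1 − t)^9.
- One patient certain to be counted as a responder: P(X ≥ 1, n = 9) = 1 − (1 − t)^9.
- Expected rise in response rate from that patient: 10 × (1 − t) points.

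| Assumed t | No carry-over | One carry-over responder | Expected rise (points) |
|---|---|---|---|
| 5% | 1 − 0.5987 − 0.3151 = 8.6% | 1 − 0.95^9 = 37% | 9.5 |
| 10% | 1 − 0.3487 − 0.3874 = 26% | 1 − 0.9^9 = 61% | 9.0 |
| 20% | 1 − 0.1074 − 0.2684 = 62% | 1 − 0.8^9 = 87% | 8.0 |
| 25% | 1 − 0.0563 − 0.1877 = 76% | 1 − 0.75^9 = 92% | 7.5 |

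**Varying the frequency instead.** Let a share c of true non-responders be counted as responders, so that the apparent rate is t + (1 − t)c. The chance of at least 2 of 10 becomes:

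| Assumed t | c = 0 | c = 5% | c = 10% | c = 20% |
|---|---|---|---|---|
| 5% | 8.6% | 25% | 44% | 73% |
| 10% | 26% | 44% | 59% | 82% |

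**The case against.** Several points on the other side have weight.

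- **Expansion is not automatic.** A reader might infer that carry-over alone would trigger it. One carry-over responder cannot meet a threshold of two. Even when two responses are seen, Section 11.4 makes expansion optional, subject to the drug company's agreement and a protocol amendment. What stands is that carry-over makes the threshold easier to reach.
- **The further-development criterion is less exposed.** Section 11.4 bases it on a rate of 30% or more of responses lasting at least 12 months. Residual shrinkage from a stopped regimen is less likely to last that long. This protects that judgement, not the primary response rate.
- **Blood counts act as a partial filter.** The neutrophil, platelet and haemoglobin limits in inclusion 6, with counts repeated if older than 72 hours, would stop some patients recently given myelosuppressive drugs. They test marrow recovery, not residual antitumour effect.
- **Exceptions are bounded.** Section 7.1 rules out exceptions that raise a safety issue or depart significantly from the scientific purpose. It still names the timing of earlier treatment as a candidate for exception.
- **Toxicity.** A reader might also infer that toxicity of the earlier regimen is charged to the combination in Cycle 1. That is possible but not built in: pre-existing conditions are recorded at baseline (Section 12.2.1), and causality is judged event by event (Sections 9.1 and 12.2.1).
- **Progression is partly a population choice.** Making it mandatory would exclude patients who changed therapy for intolerance. Reasonable statisticians could differ, so its absence alone is not an error.
- **Few patients may be affected.** The trial is an exploratory pilot, and many patients changing therapy will have progressed. That bears on likelihood; with ten patients, one case is enough to matter.

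**Conclusion.** The point holds as a gap in the entry and baseline rules. Followed exactly as written, they allow shrinkage from preceding systemic therapy to be counted in the primary response rate. Confidence is high that the rules are missing. The size of the bias is unknown, because the documents do not show how often carry-over would occur, or that it would occur at all.

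With ten patients in the denominator, one carry-over responder adds up to 10 percentage points. Under the assumed true rates of 5%, 10%, 20% and 25%, the chance of reaching 2 of 10 rises by about 28, 35, 24 and 17 points respectively. These figures assume that the patient is certain to be counted as a responder and that the other nine respond independently at the true rate.

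The documents do not support the stronger inferences that the expansion decision would be made by carry-over, that Cycle 1 toxicity would be misattributed as a rule, or that progression must be an entry criterion.

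**What to change.** 1. In Section 8.1, require the baseline tumour assessment to be done after the last dose of the most recent anticancer regimen.
2. In Section 4.3 and the synopsis, extend the interval rule already used for radiotherapy to systemic anticancer and investigational therapy. The protocol team should set the length.
3. In Section 7.1, exclude these timing rules from eligibility exceptions, because they affect the primary endpoint.
4. Record at entry whether disease progressed on or after the last regimen, and in Section 11.4 plan to report the response rate with and without patients who had not progressed. The protocol team may choose to make progression an entry criterion.

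Item 1 closes the first route, item 2 reduces the second, and item 4 shows how far the result depends on patients in whom carry-over is plausible. The cost is a short amendment; a few patients will wait, need a repeat scan, or be ineligible.
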